13.6.2. Handling of Missing Data

Element	Reporting Detail
General	• Missing data occurs when any requested data is not provided, leading to
	blank fields on the collection instrument:
	• These data will be indicated by the use of a "blank" in participant
	listing displays. Unless all data for a specific visit are missing in
	which case the data is excluded from the listing.
	• Answers such as "Not applicable" and "Not evaluable" are not
	considered to be missing data and should be displayed as such.

207546

Element	Reporting Detail
General	• Partial dates will be displayed as captured in participant listing displays.
Adverse Events	 The eCRF allows for the possibility of partial dates (i.e., only month and year) to be recorded for AE start and end dates; that is, the day of the month may be missing. In such a case, the following conventions will be applied for calculating the time to onset and the duration of the event: Missing Start Day: First of the month will be used unless this is before the start date of study treatment; in this case the study treatment start date will be used and hence the event is considered On-treatment as per Section 13.3. Missing Stop Day: Last day of the month will be used, unless this is after the stop date of study treatment; in this case the study treatment stop date will be used. Completely missing start or end dates will remain missing, with no imputation applied. Consequently, time to onset and duration of such events will be missing.
Concomitant Medications	 Partial dates for any concomitant medications recorded in the CRF will be imputed using the following convention: If the partial date is a start date, a '01' will be used for the day and 'Jan' will be used for the month If the partial date is a stop date, a '28/29/30/31' (last day of the relevant month) will be used for the day and 'Dec' will be used for the month. The recorded partial date will be displayed in listings.

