9.4.8. Participant Diary Card

Participants will be given a diary card for them to record the healing time of the blisters as well as to record any adverse events or medications taken whilst outside of the unit.

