Part A: Single Ascending Doses and LPS / GM-CSF challenges Treatment Period 1 **Treatment Period 2 Treatment Period 3** Treatment Period Cohort 1 (n=9) Cohort 1 – In Vivo 10 mg 35 mg 1 mg QD LPS Challenge + QD QD Blisters In Vivo Challenges Cohort 2 (n=9) Cohort 2 – In Vivo 45 mg 3 ma 20 mg GM-CSF Challenge QD QD QD + Blisters Evaluation of safety and tolerability plus PK and PD data review Part A Participants who are randomised into Part A can be enrolled in • Design another part of the study if they still fulfil all eligibility criteria features (which means that participants having received LPS challenge in Part A will not be eligible to participate in another part of the study). • In the Part A dose escalation phase (treatment periods 1-3), there will be two interlocking cohorts (Cohorts 1 and 2) each with up to 9 healthy participants. Each participant will receive a maximum of 2 single ascending oral doses of GSK3358699 and 1 placebo dose. At each dose level, GSK3358699 and placebo will be administered • in a 2:1 ratio, within each period, according to the randomisation schedule, in a blinded manner. Up to a maximum of 6 dose levels will be studied in total in Part A. Participants who are enrolled in the dose escalation treatment Periods of Part A may choose to only take part in the dose escalation treatment Periods 1-3, or may choose to also take part in the challenge treatment period (Period 4). If a participant chooses to participate in the dose escalation treatment Periods 1-3 only, or does not (at screening) meet the eligibility criteria specific to challenges (treatment Period 4), a new participant

The table below provides an overview of the study design and the key features.

e Ascending Doses and LPS / GM-CSF challenges

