13.3. Appendix 3: Study Phases and Treatment Emergent Adverse Events

13.3.1. Study Phases for Parts A and C

Assessments and events will be assigned to the relevant treatment Period dependent on whether they are spontaneous events (i.e. data collected in a log such as Adverse Events and Concomitant Medications, and Disposition) or planned events (i.e. data with timeslicing assigned such as ECG, Laboratory, and Vital Signs).

Spontaneous events are assigned to period according to the time of occurrence relative to the start date/time of the study treatment within the period up to, but not including, the start date/time of the study treatment in the next period. Planned assessments, including unscheduled visits are assigned to period according to the date of first visit of that period (including Day -1 and Day -10 assessments as applicable) up to the day prior to the first visit of the next period or day prior to Follow-Up visit (including Day -1 and Day -10 assessments as applicable).

For planned events, assessments prior to the date of first visit in Period 1 for Part A (or Period 7 for Part C) are assigned as Screening. For spontaneous events, events prior to the datetime of first dose in Period 1 for Part A are assigned as Pre-Treatment (or Period 7 for Part C).

For planned events, assessments on or later than date of first Follow-Up visit are assigned as Follow-Up. For spontaneous events, events later than date of last dose + 7 days are assigned as Follow-Up.

Study Phase	Definition
Prior	If medication end date is not missing and is before 28 days prior to
	screening visit
Concomitant	Any medication that is not a prior
1. NOTE:	

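### The partial-date rule caps an AE stop date at the treatment stop date with no floor at onset, so some AEs end before they begin; the Part A reference date for partial onsets is also undefined

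*SAP*

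**What the plan says.** SAP 13.6.2.1 (Handling of Missing and Partial Dates, Adverse Events) notes that the eCRF allows AE start and end dates with month and year only. It gives the purpose of the imputation: "the following conventions will be applied for calculating the time to onset and the duration of the event". For a missing stop day: "Last day of the month will be used, unless this is after the stop date of study treatment". When month-end is the later of the two, the imputed end becomes the day treatment stopped. For a missing start day: "First of the month will be used unless this is before the start date of study treatment", in which case the treatment start date is used and the event counts as on-treatment under SAP 13.3. The same section adds: "Partial dates will be displayed as captured in participant listing displays".

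Four other places bear on how the rule works:

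- SAP 2.3, Part A: "Each participant will receive a maximum of 2 single ascending oral doses of GSK3358699 and 1 placebo dose". Each period is a single dose, and doses within a cohort are at least 28 days apart (Protocol 5.1.1.3).
- Protocol 9.2.1: AEs are collected from the start of treatment until the follow-up visit. Follow-up is 7 to 14 days after the last dose, with a second visit at about 5 weeks in challenge cohorts. Protocol 9.4.8 gives participants a diary card to "record any adverse events or medications taken whilst outside of the unit".
- SAP 13.3.1: "Spontaneous events are assigned to period according to the time of occurrence", running from a period's dose up to the next period's dose.
- SAP 13.3.2: the treatment-emergent window extends one day past treatment stop. For a Part A AE that worsens in a later period, that period's own treatment dates apply.

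**The concern.** A cap at treatment stop is workable only if AEs do not begin after treatment stops. Here they are expected to. Part A treatment lasts one day per period, AE collection continues to follow-up, and the SAP itself treats an onset on the day after treatment stop as treatment-emergent. With no floor at onset, the rule can produce an end date before a known start date, and so an impossible value of the very quantity it exists to calculate.

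The start-day rule has a different weakness. In a crossover with up to four doses per participant, the start date of study treatment could be the period's dose or the first dose of all. The rule does not choose, and the choice decides whether a partly dated onset can fall before the dose it followed. AE reporting is a primary endpoint, so the dating rules should be unambiguous even if few records need them.

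**Working it through.** The SAP states no figure on this point, so there is nothing to reproduce. The rule is applied as written. All calendar dates are illustrative assumptions.

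**Stop day, general case.** Let D be the treatment stop date, S the known onset and M the last day of the recorded stop month. The rule gives E = min(M, D), and duration = E - S + 1. If S is later than D, the AE ends on or after S, so M is at or after S and therefore after D. The cap always binds: E = D, E precedes S, and the duration is D - S + 1, which is 0 or less.

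**Stop day, Part A with D as the period's dosing day.** Dose 5 June, stop recorded as June, so E = min(30 June, 5 June) = 5 June:

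- onset 5 June: 5 - 5 + 1 = 1 day (not reversed)
- onset 7 June: 5 - 7 + 1 = -1 day
- onset 12 June: 5 - 12 + 1 = -6 days

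A grid check agrees. It took a first dose on each of 365 days, three periods 28 days apart, onset 1 to 27 days after the dose, and true stops 0, 1, 3 or 7 days after onset: 365 x 3 x 27 x 4 = 118,260 cases. All 118,260 end before they start.

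**Stop day, Part A with D as the last dose of all.** Only last-period cases can have S after D: 365 x 27 x 4 = 39,420, and all of them reverse. None reverses in earlier periods.

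**Part C.** There is one treatment period, so the two readings coincide. Any AE with onset after the last dose reverses by the same algebra.

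**With the cap removed and a floor at onset.** E = max(S, M) gives 0 reversals in the same 118,260 cases. Adding an upper limit at last study contact inside the floor, E = max(S, min(M, last contact)), cannot create one, because E is never below S.

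**Start day, floor at the first dose.** First dose 10 June, Period 2 dose 8 July, onset recorded as July. The imputed onset is 1 July, which is after 10 June, so the floor does not act. It is also before 8 July, so SAP 13.3.1 would place the event in Period 1 if imputed dates are used there. An onset in Period 2 recorded as August becomes 1 August and stays in Period 2 (Period 3 dose 5 August).

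Over the grid (365 x 2 x 28 = 20,440 Period 2-3 onsets, days 0 to 27), 10,696 (52%) move back one period. By time since dose the shares are 87% (days 0-6), 64% (days 7-13), 41% (days 14-20) and 18% (days 21-27). These are counts over evenly spread dates, not forecasts.

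**Start day, floor at the period's dose.** Nothing moves, but the rule is circular: the floor needs the period, and SAP 13.3.1 gets the period from the onset time.

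**Where a moved event would go.** The Period 1-3 sequences are PCE, APE, ACP (Cohort 1) and PDF, BPF, BDP (Cohort 2), which give six transitions per cohort. The earlier treatment is a lower active dose in 2, placebo in 2, and active drug while the current treatment is placebo in 2. In Period 4, 25 mg follows 40 mg or 30 mg in two of the three sequences of each cohort and placebo in the third.

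**The case against.** The strongest reply is that the practical reach is small, and most of that stands. The imputation is stated to serve time to onset and duration. The listed AE tables (2.1 to 2.8 and 2.23 to 2.30) and figures are incidence displays, and no display title names either quantity. Shells are held separately (SAP 13.9.2), so a duration column cannot be ruled out, but no planned summary is shown to change. Capping a stop date cannot alter AE incidence. Listings show the date as recorded. Participants are in the unit until about 48 hours after a Part A dose, and a diary card may improve dating. The number of partial dates could be zero, and a negative duration would be visible to a programmer.

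It can also be said that the two limbs need opposite readings to reach full extent: the stop-day fault is widest with period-specific dates, while the start-day shift needs the first dose. That is correct. SAP 13.3.2 favours period-specific dates, on which onsets do not move. Use of imputed dates for period assignment is itself an inference, resting on the cross-reference to SAP 13.3.

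A reader might infer that the rule credits events to a lower dose, or that with six active participants per dose one moved event shifts a dose-level rate by 1/6 = 16.7 points. The documents do not support this. It needs the less-favoured reading plus that inference, and the earlier treatment is a lower active dose in only 2 of 6 Period 1-3 transitions. Nor are events late in a period the ones mainly displaced; those soon after a dose are.

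None of this removes the missing floor at onset.

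**Conclusion.** The stop-day rule is defective as written; this is more than missing detail. With period-specific dates, every Part A AE with a known onset after the dosing day and a month-and-year stop gets an end before its start. With the last dose as the reference, the same holds for AEs beginning after it. In Part C it holds on either reading for onsets after the last dose. The start-day rule is ambiguous for the crossover: one reading can place a Period 2-4 onset before its own dose when onset and dose share a calendar month, and the other is circular without a period-assignment rule.

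The severity is minor. The effect is confined to AEs with partial dates, whose number is not given, and no effect on the planned AE incidence displays is demonstrated. The conclusion on stop dates assumes that the rule is programmed literally. The conclusion on period shifts further assumes the first-dose reading and use of imputed dates in SAP 13.3.1.

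**What to change.** In SAP 13.6.2.1:

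1. Delete the cap at the treatment stop date. Impute a missing AE stop day as the earlier of month-end and the participant's last study contact, and never earlier than AE onset.
2. State that in Part A the start-day floor uses the period-specific treatment dates, as SAP 13.3.2 does for worsening AEs.
3. State how a partly dated onset is assigned to a period when a dose was given in the recorded month. Always choosing the latest dose in that month would pull some AEs from the preceding washout onto the new dose, so the rule should say how a known AE end date is used and which period applies when the order remains unknown.

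The cost is a few sentences and a small derivation change. No new data are needed.

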13.6.2.1. Handling of Missing and Partial Dates

207546

13.7. Appendix 7: Values of Potential Clinical Importance and Normal Ranges

13.7.1. Vital Signs

Vital Sign Parameter	Units	Clinical Concern Range	
(Absolute)		Lower	Upper
Systolic Blood Pressure	mmHg	< 85	> 160
Diastolic Blood Pressure	mmHg	< 45	> 100
Heart Rate	bpm	< 40	> 110
Respiratory Rate	breaths/min	< 11	> 20
Temperature	°C	< 35.5	> 38.0

13.7.2. Laboratory Values

Hematology – PCI Criteria			
Laboratory Parameter	Units	Clinical Concern Range	
		Low Flag (< x)	High Flag (>x)
Hematocrit	Ratio of 1		0.54
Hemoglobin	g/L		180
Lymphocyte Count	x10 ⁹ / L	0.8	
Neutrophil Count	x10 ⁹ / L	1.5	
Platelet Count	x10 ⁹ / L	100	550
White Blood Cell Count (WBC)	x10 ⁹ / L	3	20

Hematology – Normal Ranges			
Laboratory Parameter	Units	Normal Range	
		Low Flag (< x)	High Flag (>x)
Activated Partial Thromboplastin Time (APTT)	secs	25	37
Basophil Count	x10 ⁹ / L	0.0	0.1
Eosinophil Count	x10 ⁹ / L	0.0	0.4
Fibrinogen	g/L	1.5	4.0
Mean Corpuscle Hemoglobin (MCH)	pg	26.0	33.5
Mean Corpuscle Volume (MCV)	fL	80	99
Monocyte Count	x10 ⁹ / L	0.2	1.0

207546 | Statistical Analysis Plan RAP 22 Jun 2020 | TMF-1817519 | 1.0

CONFIDENTIAL

Hematology – Normal Ranges			
Laboratory Parameter	aboratory Parameter Units Normal Range		l Range
		Low Flag (< x)	High Flag (>x)
Prothrombin Time (PT)	secs	10	12
Red Blood Cell Count (RBC)	x10 ¹² / L	4.4	5.8
Reticulocyte Count	%	0.38	2.64

Clinical Chemistry – PCI Criteria			
Laboratory Parameter	Units	Clinical Concern Range	
		Low Flag (< x)	High Flag (>x)
Albumin	G/L	30	
Calcium	mmol/L	2	2.75
Creatinine	mmol/L		1.3 X ULN
Glucose	mmol/L	3	9
Potassium	mmol/L	3	5.5
Sodium	mmol/L	130	150

Clinical Chemistry – Normal Ranges			
Laboratory Parameter	Units	Normal Range	
		Low Flag (< x)	High Flag (>x)
Alanine Aminotransferase (ALT)	IU/L	10	50
Alkaline Phosphatase (ALP)	IU/L	40	129
Aspartate Aminotransferase (AST)	IU/L	0	37
Blood Urea Nitrogen (BUN)	mg/dL	4.76	23.24
C-reactive Protein	mg/L	0.0	5.0
Cholesterol	mmol/L	2.3	4.9
Direct Bilirubin	umol/L	0	5
High Density Lipoprotein	mmol/L	0.9	1.5
Low Density Lipoprotein	mmol/L	0	3.0
Total Bilirubin	umol/L	0	20
Total Protein	g/L	63	83
Triglycerides	mmol/L	0	2.3

207546

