8.1.3. Haematological Stopping Criteria

A participant that meets the criteria below, where the finding is persistent, confirmed on repeat testing and is regarded as clinically significant by the Investigator, will be withdrawn from the study. It should be noted that following acute LPS or GM-CSF challenge transient changes in haematological criteria are expected. Since the challenges are only administered after the final dose of GSK3358699 in any given part of the study, haematological results following challenge administration will be reviewed and any action based on evaluation of results will be at Investigator discretion in conjunction with the Medical Monitor.

- Haemoglobin \leq 9 g/dL (5.58 mmol/L) or an absolute decrease of \geq 3 g/dL from baseline (pre-dose Day 1)
- Neutrophils $\leq 1.0 \ge 10^{9}/L$, or neutrophils $> 1.0-1.5 \ge 10^{9}/L$ if the results are deemed clinically significant at the discretion of the Investigator.
- Lymphocytes $\leq 0.5 \times 10^9/L$
- Platelets $\leq 50,000/\text{mm}^3$

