2.13.	Safety	LB17	Part A: Summary of Worst Case Hematology Results by PCI Criteria Post-Baseline Relative to Baseline	Order parameters alphabetically, include parameters with PCI criteria listed in Appendix 7.	SAC		
2.14.	Safety	LB15	Part A: Summary of Worst Case Hematology Results Relative to Normal Range Post-Baseline Relative to Baseline	Order parameters alphabetically, include parameters with Normal Ranges listed in Appendix 7.	SAC		
ECG	1	1		1	1		
2.15.	Safety	EG1	Part A: Summary of ECG Findings	Crossover part: counts and percentages are based on the number of subjects in each treatment, so participants will appear in multiple treatments.	SAC		
2.16.	Safety	EG10	Part A: Summary of Maximum QTcF Values Post- Baseline Relative to Baseline by Category	Crossover part: counts and percentages are based on the number of subjects in each treatment, so participants will appear in multiple treatments.	SAC		
2.17.	Safety	EG11	Part A: Summary of Maximum Increase in QTcF Values Post-Baseline Relative to Baseline by Category	Crossover part: counts and percentages are based on the number of subjects in each treatment, so participants will appear in multiple treatments.	SAC		

Safety	Safety: Tables						
No.	Population	IDSL / Example Shell	Title	Programming Notes	Deliverable [Priority]		
2.18.	Safety	EG2	Part A: Summary of Change from Baseline in ECG Values by Visit	Crossover part: counts and percentages are based on the number of subjects in each treatment, so participants will appear in multiple treatments.	SAC		
Holter	•	•	•				
2.19.	Safety	HM1	Part A: Summary of Holter Interpretations		SAC		
2.20.	Safety	HM2	Part A: Summary of Holter Abnormalities		SAC		
Vital S	Signs						
2.21.	Safety	VS1	Part A: Summary of Change from Baseline in Vital Signs	Crossover part: counts and percentages are based on the number of subjects in each treatment, so participants will appear in multiple treatments.	SAC		
2.22.	Safety	VS7	Part A: Summary of Worst Case Vital Sign Results by PCI Criteria Post-Baseline Relative to Baseline	Crossover part: counts and percentages are based on the number of subjects in each treatment, so participants will appear in multiple treatments.	SAC		

Safety	y: Tables				
No.	Population	IDSL / Example Shell	Title	Programming Notes	Deliverable [Priority]
Adve	rse Events (Al	Es)			
2.23.	Safety	AE5a	Part C: Summary of All Adverse Events by Maximum Intensity by System Organ Class and Preferred Term	Include total column.	SAC

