13.9.11. ICH Listings

Part A

ICH	ICH: Listings							
No.	Population	IDSL / Example Shell	Title	Programming Notes	Deliverable [Priority]			
Sub	Subject Disposition							
1.	Screened	ES7	Part A: Listing of Reasons for Screen Failure		SAC			
2.	Safety	ES3	Part A: Listing of Reasons for Study Withdrawal		SAC			
3.	Safety	BL2	Part A: Listing of Subjects for Whom the Treatment Blind was Broken		SAC			
4.	Safety	TA1	Part A: Listing of Planned and Actual Treatment		SAC			
Prot	Protocol Deviations							
5.	Safety	DV2a	Part A: Listing of Important Protocol Deviations		SAC			

ICH	: Listings				
No.	Population	IDSL / Example Shell	Title	Programming Notes	Deliverable [Priority]
6.	Safety	IE4	Part A: Listing of Subjects with Inclusion/Exclusion Criteria Deviations		SAC
Dem	ography	·			·
7.	Safety	DM4	Part A: Listing of Demographic Characteristics		SAC
8.	Safety	DM10	Part A: Listing of Race		SAC
Pop	ulations Analys	ed			
9.	Screened	SP3a	Part A: Listing of Subjects Excluded from Any Population		SAC
Con	comitant Medic	cations			
10.	Safety	CM5	Part A: Listing of Concomitant Medications		SAC
Exp	osure	·	·		
11.	Safety	EX4	Part A: Listing of Exposure Data		SAC
Adv	erse Events				
12.	Safety	AE9CP	Part A: Listing of All Adverse Events		SAC
13.	Safety	AE7	Part A: Listing of Subject Numbers for Individual Adverse Events		SAC
14.	Safety	AE2	Part A: Listing of Relationship Between Adverse Event System Organ Classes, Preferred Terms, and Verbatim Text		SAC
15.	Safety	AE14	Part A: Listing of Reasons for Considering as a Serious Adverse Event		SAC
16.	Safety	AE9CPa	Part A: Listing of Serious Adverse Events		SAC
17.	Safety	AE9CP	Part A: Listing of Adverse Events Leading to Permanent Discontinuation of Study Treatment or Withdrawal from Study		SAC

ICH	ICH: Listings							
No.	Population	IDSL / Example Shell	Title	Programming Notes	Deliverable [Priority]			
Lab	oratory							
18.	Safety	LB6	Part A: Listing of All Laboratory Data for Subjects with Any Value Outside of Normal Range or of Potential Clinical Importance		SAC			
19.	Safety	LB6	Part A: Listing of All Laboratory Values Outside of Normal Range or of Potential Clinical Importance		SAC			
20.	Safety	LB14	Part A: Listing of Laboratory Data with Character Results		SAC			
21.	Safety	UR2B	Part A: Listing of Urinalysis Data for Subjects with Any Value of Potential Clinical Importance		SAC			
22.	Safety	MH2	Part A: Listing of Medical Conditions for Subjects with Liver Stopping Events		SAC			

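### Haemoglobin has only a high flag in SAP Appendix 7, so a fall meeting the protocol's withdrawal threshold is counted in no worst-case haematology table

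*SAP*

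**What the plan says.** SAP Appendix 7 (section 13.7.2) holds two haematology tables. Under "Hematology – PCI Criteria" the haemoglobin row is "Hemoglobin g/L 180": the low cell is empty and 180 is the high limit. Under "Hematology – Normal Ranges" the rows are APTT, basophils, eosinophils, fibrinogen, MCH, MCV, monocytes, PT, RBC and reticulocytes. Haemoglobin is not among them.

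SAP section 13.9.5 ties the worst-case tables to that appendix. Table 2.13, "Part A: Summary of Worst Case Hematology Results by PCI Criteria Post-Baseline Relative to Baseline", and its Part C counterpart 2.35 use the PCI criteria. Tables 2.14 and 2.36 take only parameters with a normal range there. In section 13.9.11, Listing 19 is "Part A: Listing of All Laboratory Values Outside of Normal Range or of Potential Clinical Importance", and Listing 52 is its Part C counterpart. Listings 18 and 51 are wider: they give the complete laboratory data of any subject who has at least one such value.

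Protocol section 8.1.3 sets the haemoglobin threshold at or below "9 g/dL (5.58 mmol/L) or an absolute decrease of" at least "3 g/dL from baseline (pre-dose Day 1"). Withdrawal also requires that the finding lasts, is reproduced on a second test and is judged clinically meaningful by the investigator.

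**The concern.** The protocol is concerned with haemoglobin going down; the SAP flags it only going up. Laboratory safety, including haematology, belongs to the primary objective. The worst-case tables are where a reader looks for individual extremes that group means hide. With the flags as written, a participant whose haemoglobin had crossed a withdrawal threshold would be counted there as having no haemoglobin value of concern.

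The gap looks like an omission. Appendix 7 gives low limits for the other three cell counts named in protocol section 8.1.3. In section 13.7.3 it also mirrors a change-from-baseline withdrawal criterion: the QTcF increase above 60 msec, which matches protocol section 8.1.2.

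**Working it through.** **Is the empty low cell real?** The row has the same shape as other one-sided rows, such as creatinine (high only), and 180 g/L makes no sense as a low limit. I take the cell as intentionally blank and not as extraction damage.

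**Units.** 9 g/dL × 10 = 90 g/L. 3 g/dL × 10 = 30 g/L.

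**Protocol thresholds against SAP low flags.**

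| Parameter | Protocol 8.1.3 | SAP low PCI flag | Covered? |
|---|---|---|---|
| Neutrophils (×10⁹/L) | ≤ 1.0 | < 1.5 | yes |
| Lymphocytes (×10⁹/L) | ≤ 0.5 | < 0.8 | yes |
| Platelets (×10⁹/L) | ≤ 50 | < 100 | yes |
| Haemoglobin (g/L) | ≤ 90, or fall ≥ 30 | none (high flag > 180 only) | no |

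**Can another red-cell row catch it?** By definition MCH is haemoglobin divided by red cell count, so Hb (g/L) = RBC (×10¹²/L) × MCH (pg). The documents do not state this identity. SAP normal ranges: RBC 4.4 to 5.8, MCH 26.0 to 33.5.

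*Absolute threshold.* The lowest haemoglobin with both in range is 4.4 × 26.0 = 114.4 g/L. At 90 g/L, an in-range MCH implies RBC between 90/33.5 = 2.69 and 90/26.0 = 3.46, both low. If RBC is at least 4.4, MCH is at most 90/4.4 = 20.5, also low. One of the two must be flagged.

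*Fall of 30 g/L.* At constant MCH the RBC drop is 30/MCH. To stay at or above 4.4 afterwards, baseline RBC must be at least 4.4 + 30/MCH:

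| MCH (pg) | RBC drop | Lowest baseline RBC |
|---|---|---|
| 26 | 1.15 | 5.55 |
| 28 | 1.07 | 5.47 |
| 30 | 1.00 | 5.40 |
| 32 | 0.94 | 5.34 |
| 33.5 | 0.90 | 5.30 |

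All are below the upper limit of 5.8, so the fall can happen with neither row flagged. Example: 165 to 135 g/L at MCH 29.5 gives RBC 165/29.5 = 5.59 and 135/29.5 = 4.58. Both are in range, and 165 is below the 180 flag.

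**Would the group summary show it?** Tables 2.12 and 2.34 summarise change from baseline. One fall of 30 g/L among the six active participants at a Part A dose moves the mean by 30/6 = 5 g/L. The mean change would not show that one person crossed the threshold.

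**The case against.** The strongest reply is that the data are not lost, and most of it stands.

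- A reader might infer that the fall appears in no listing. The documents do not support that: Listings 18 and 51 print every laboratory result for a subject with any flagged value, haemoglobin included. At 90 g/L or below, RBC or MCH must be out of range, so the subject enters Tables 2.14/2.36 (if the visit is scheduled) and, if the listings use Appendix 7 limits, the listings too.
- A reader might infer that any large fall escapes. It does not. At 115 g/L, RBC and MCH are both in range only if MCH lies between 26.0 and 115/4.4 = 26.14 pg.
- A reader might infer that a withdrawal would leave no trace. Reasons for withdrawal are in Listings 2 and 35, clinically relevant laboratory changes are recorded as adverse events (protocol section 9.4.7), and events leading to withdrawal have Tables 2.6/2.26 and Listings 17/50.
- A reader might infer that the SAP flags the wrong direction for a named risk. The haematologic entry in protocol section 3.3.1 names variable red-cell changes and platelet decreases, not a haemoglobin fall.
- Haematocrit has the same one-sided row ("Hematocrit Ratio of 1 0.54"), but the protocol sets no haematocrit stopping limit, so the argument does not carry over.

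None of this fills the worst-case tables. It shows that the information can be recovered elsewhere, mostly by reading individual data.

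**Conclusion.** The point holds as a reporting gap of modest size. No worst-case table can count a haemoglobin fall, and haemoglobin alone among the four haematology criteria lacks a matching flag. The absolute threshold still surfaces indirectly. The 30 g/L fall can pass every haematology flag when baseline RBC is about 5.30 to 5.55 or higher (depending on MCH), up to 5.8. The documents give no RBC distribution, so how often that would happen cannot be stated.

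Assumptions:
- MCH is stable across the fall.
- The other haematology rows, including reticulocytes and MCV, stay unflagged.
- Listings 18, 19, 51 and 52 use the Appendix 7 limits. That is the natural reading, but the explicit instruction is attached to the tables only.

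Even in the escaping case, an out-of-range value on any other laboratory test brings the subject's haemoglobin into Listing 18 or 51, though not flagged.

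**What to change.** Add two haemoglobin reporting flags to Appendix 7 at the limits already in protocol section 8.1.3: 90 g/L or below, and a decrease of 30 g/L or more from baseline. Write them as inclusive limits, because the Appendix 7 low flags are strict inequalities. Say that baseline is the one defined in SAP section 5.3. Add the laboratory's haemoglobin normal range; the documents do not give its figures. State that the listings use Appendix 7. Then re-run Tables 2.13, 2.14, 2.35 and 2.36 and Listings 18, 19, 51 and 52.

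This changes reporting only, not clinical management. The flags mark that the numerical threshold was crossed, not that the full withdrawal criterion was met. Unscheduled repeats remain outside the summary tables under SAP section 8.2 and appear only in listings. The cost is an appendix edit, a re-run of standard outputs and a few more flagged values to review, some of them due to blood sampling and also seen on placebo.

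A minor addition is to give ranges for GGT and CK, which Amendment 4 added for monitoring and which have no limit of either kind. This matters mainly for Part C: the Part A schedule carries no note for them, and they are measured only at screening, Day -1 and follow-up.
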